**Table 5.15**

| Worst toxicity (CTCAE 4.03 Grade)*   | Dose Modifications for trametinib  |
|---|---|
| BRADYCARDIA  |   |
| Grade 1 or Grade 2  | Omit dose until recovery to asymptomatic bradycardia or to a heart rate $\geq$ 60 bpm
Evaluate concomitant medications known to cause bradycardia and adjust the dose of trametinib  |
| Grade 3
Grade 4 (in patients taking a concomitant medication also known to cause bradycardia or a medication known to cause hypotension)   | Omit dose until recovery to asymptomatic bradycardia or to a heart rate $\geq$ 60 bpm
If the concomitant medication can be adjusted or discontinued, resume trametinib at $\downarrow$ 1 dose level with frequent monitoring |
| Grade 4 (in patients who are not taking a concomitant medication also known to cause bradycardia or known to cause hypotension)   | Permanently discontinue trametinib  |
| PANCREATIC   |   |
| Amylase and/or lipase elevations (in the absence of clinical symptoms)   |   |
| Grade 1 ( $>$ ULN and $\leq$ 1.5 x ULN)   | Maintain dose level   |
| Grade 2 ( $>$ 1.5 - 2.0 x ULN)  | Maintain dose level   |
| Grade $\geq$ 3 ( $>$ 2.0 x ULN)   | Omit dose until resolved to $\leq$ Grade 1, then $\downarrow$ 1 dose level  |
| Note: Withhold trametinib for acute onset of new or progressive unexplained abdominal symptoms, such as severe pain or vomiting; perform diagnostic procedures (e.g., abdominal CT scan or ultrasound) to exclude pancreatic pathology. |   |

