**Table 5.3 Dose Delay and Modification for Events Considered Related to Trametinib**

| CTCAE Grade | Action and Dose Modification  |
|-------------|---|
| Grade 1     | 
 
Continue trametinib at current dose level
 
Monitor closely
 
Provide supportive care according to institutional standards
 
  |
| Grade 2     | 
 
Interrupt trametinib if clinically indicated
 
Monitor closely
 
Provide supportive care according to institutional standards
 
When toxicity resolves to Grade 1 or baseline, restart trametinib at current dose level
 
  |
| Grade 3     | 
 
Interrupt trametinib if clinically indicated
 
Monitor closely
 
Provide supportive care according to institutional standards
 
When toxicity resolves to Grade 1 or baseline, restart trametinib reduced by one dose level
 
If the Grade 3 toxicity recurs, interrupt trametinib
 
When toxicity resolves to Grade 1 or baseline, restart trametinib reduced by another dose level
 
 |
| Grade 4     | 
 
Interrupt trametinib
 
Monitor closely
 
Provide supportive care according to institutional standards
 
If event resolves to Grade 1 or baseline discuss potential continuation of trametinib with investigator-sponsor; if continuation of treatment agreed then restart trametinib at dose reduced by one dose level
 
If event does not resolve permanently discontinue trametinib
 
       |

**Note:** Approval from the investigator-sponsor is required to restart study treatment after ≥ 28 days of interruption.

Trametinib dose modification guidelines are outlined in Table 5.2 and Table 5.3 for clinically significant toxicities that are deemed related to trametinib (i.e. peripheral and periorbital edema) with the exception of the **following events of special interest**:

- rash (Section 5.2.1)
- diarrhea (Section 5.2.2),
- ejection fraction changes (Section 5.2.3),
- hypertension (Section 5.2.4)
- prolonged QTc (Section 5.2.5)
- pneumonitis (Section 5.2.6),
- visual changes (Section 5.2.7),
- liver chemistry elevation (Section 5.2.8)

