**For these, refer to the relevant sections for dose modification guidelines for adverse events of special interest.**

Treatment or visit delays for public holidays or weather conditions do not constitute a protocol violation.

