### 5.2.9 Guidelines for other toxicity

**Table 5.14**

| Worst toxicity (CTCAE 4.03 Grade)*  | Dose Modifications for trametinib  |
|--|---|
| GENERAL DISORDERS   |   |
| Fatigue (asthenia)  |   |
| Grade 1 or 2   | Maintain dose level   |
| Grade 3  | If grade 3 fatigue resolves to Grade 2 in ≤ 7 days, maintain dose level
If grade 3 fatigue lasts > 7 days, omit dose until resolved to ≤ Grade 2 and then ↓ dose level   |
| PULMONARY   |   |
| Notes:   |   |
| 
 
• Withhold trametinib for acute onset of new or progressive unexplained pulmonary symptoms, such as dyspnea, cough and fever and during diagnostic workup for pneumonitis/ILD.
 
• During evaluation of potential grade 2, 3, and 4 pneumonitis, if an infectious etiology is confirmed (i.e., pneumonia) and pneumonitis is excluded, then consider resuming at current dose level after the pneumonia resolves.
 
 |   |
| PNEUMONITIS   |   |
| Worst toxicity (CTCAE 4.03 Grade)*  | Dose Modifications for trametinib  |
| Any Grade treatment-related ILD/pneumonitis  | Permanently discontinue patient from study.   |
| CARDIAC INVESTIGATIONS  |   |
| Electrocardiogram QT corrected (QTc) interval prolonged   |   |
| Grade 1 (QTc 450-480 ms)
Grade 2 (QTc 481-500 ms)   | Maintain dose level   |
| Grade 3 (QTc ≥ 501 ms on at least two separate ECGs)   | Omit dose until QTC is less than 481 ms, then ↓ dose level
Perform an analysis of serum potassium, and if below lower limit of normal, correct with supplements to within normal limits.
-Repeat ECG in 24 hours, or less, as clinically indicated; continue monitoring as clinically indicated until QTc < 481 ms
-Repeat ECGs 7 days after dose resumption for all patients who had therapy interrupted due to QTc ≥ 501 ms. |
| Grade 4 (QTc ≥ 501 or > 60ms change from baseline and Torsades de pointes or polymorphic ventricular tachycardia or signs/symptoms of serious arrhythmia)  | Permanently discontinue patient from trametinib.  |

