## 7.4 Recording of an Adverse Event

All grade 3 and above adverse events will be entered into OnCore®, whether or not the event is believed to be associated with use of the study drug. Data about these events and their severity will be recorded using the NCI CTCAE v4.03.

The Investigator will assign attribution of the possible association of the event with use of the investigational drug, and this information will be entered into OnCore® using the classification system listed below:

| Relationship                            | Attribution | Description                                       |
|--|--------------------|--|
| Unrelated to investigational drug/intervention | Unrelated          | The AE is clearly NOT related to the intervention |
|  | Unlikely           | The AE is doubtfully related to the intervention  |
| Related to investigational drug/intervention   | Possible           | The AE may be related to the intervention         |
|  | Probable           | The AE is likely related to the intervention      |
|  | Definite           | The AE is clearly related to the intervention     |

Signs or symptoms reported as adverse events will be graded and recorded by the Investigator according to the CTCAE. When specific adverse events are not listed in the CTCAE they will be graded by the Investigator as *none*, *mild*, *moderate* or *severe* according to the following grades and definitions:

- Grade 0 No AE (or within normal limits)
- Grade 1 Mild; asymptomatic or mild symptoms; clinical or diagnostic observations only; intervention not indicated
- Grade 2 Moderate; minimal, local, or noninvasive intervention (e.g., packing, cautery) indicated; limiting age-appropriate instrumental activities of daily living (ADL)
- Grade 3: Severe or medically significant but not immediately life-threatening; hospitalization or prolongation of hospitalization indicated; disabling; limiting self-care ADL
- Grade 4: Life-threatening consequences; urgent intervention indicated
- Grade 5: Death related to AE

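### Fatigue and bradycardia fall under both Table 5.3 and Section 5.2.9, no text says which governs, and the two conflict for Grade 3 fatigue and for Grade 4 bradycardia with no contributing drug

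*Combined protocol and SAP*

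**What the plan says.** The text under Table 5.3 in Section 5.2 gives the general scope: "Trametinib dose modification guidelines are outlined in Table 5.2 and Table 5.3 for clinically significant toxicities that are deemed related to trametinib". It then lists eight exceptions, from rash (Section 5.2.1) to "liver chemistry elevation (Section 5.2.8"). For those eight, the reader is told to "refer to the relevant sections for dose modification guidelines for adverse events of special interest". Section 5.2.9 is not on the list.

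Section 5.2.9 nevertheless carries event-specific rules. For fatigue, Table 5.14 says "If grade 3 fatigue resolves to Grade 2 in ≤ 7 days, maintain dose level"; if Grade 3 lasts longer, the dose is omitted until Grade 2 or lower and then reduced. For Grade 1 or 2 bradycardia, Table 5.15 says "Omit dose until recovery to asymptomatic bradycardia or to a heart rate" of at least 60 bpm, and adds that the trametinib dose should be adjusted, without giving a direction or size. For the row headed "Grade 4 (in patients who are not taking a concomitant medication also known to cause bradycardia or known to cause hypotension"), the action is permanent discontinuation. Table 5.15 also covers raised amylase or lipase without symptoms, likewise absent from the exception list.

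**The concern.** An explicit list of exceptions implies that everything not listed stays under the general rule. Fatigue and bradycardia are not listed, yet each has its own table. A site that turns to Table 5.3 and a site that turns to Section 5.2.9 can therefore treat the same event differently while each believes it is following the protocol.

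At Grade 4 this is a patient-safety matter. It also affects reporting. Treatment-emergent events that lead to discontinuation, and those that lead to interruption, reduction or delay, are secondary safety endpoints in Section 2.4.2 and are tabulated under Section 8.3.3. In a multicenter trial of 27 patients, those counts would partly reflect which table a site consulted.

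**Working it through.** No formula applies and the plan gives no figure to reproduce. The check has three steps.

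**Step 1: does any text settle precedence?** The redirect after Table 5.3 covers only the eight listed events. Section 5.3 ties dose adjustment to the organ system with the worst toxicity; that chooses between systems, not between two tables for one event. No other text ranks the tables.

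**Step 2: the two rule sets side by side**, for events that are related and clinically significant.

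| Event | Table 5.3 | Section 5.2.9 | Result |
|---|---|---|---|
| Grade 4 bradycardia, no contributing drug | Interrupt; once at Grade 1 or baseline, discuss with the investigator-sponsor and, if agreed, restart one level lower | Permanent discontinuation | Conflict |
| Grade 3 fatigue, Grade 2 within 7 days | Interrupt if clinically indicated; after an interruption, restart only at Grade 1 or baseline, one level lower | Dose maintained | Conflict once dosing has been interrupted |
| Grade 3 fatigue beyond 7 days | As above | Omit until Grade 2 or lower, then reduce | Both restart at a reduced dose; restart threshold differs by one grade |
| Grade 3 bradycardia | Interrupt if clinically indicated; restart one level lower at Grade 1 or baseline | Omit; resume one level lower if the concomitant drug can be changed | Same dose step, different conditions |
| Grade 3 or higher amylase/lipase | Grade 3: restart one level lower at Grade 1 or baseline. Grade 4: the same, after discussion with the investigator-sponsor | Omit until Grade 1 or lower, then one level lower | Same dose step; only Table 5.3 adds the Grade 4 discussion |

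In the second row, a patient on the starting dose whose short episode was interrupted would go back to 2 mg under Table 5.14 and to 1.5 mg under Table 5.3 (dose levels from Table 5.2).

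**Step 3: Table 5.15 on its own.** Two faults remain whichever table governs.

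- *Grade 1 or 2.* Recovery means either asymptomatic bradycardia or a heart rate of at least 60 bpm. An asymptomatic event meets the first alternative at onset, so the instruction to omit ends as it begins. The documents do not reproduce the CTCAE bradycardia entry. The fallback scale in Section 7.4 describes Grade 1 as "Mild; asymptomatic or mild symptoms; clinical or diagnostic observations only; intervention not indicated", so on that scale a Grade 1 event may also carry mild symptoms, and for such a patient the condition does work.
- *Grade 3, no contributing drug.* Resumption depends on changing a concomitant drug. If the row's parenthesis applies only to Grade 4, these patients are told to omit the dose but not how to resume. If it applies to Grade 3 as well, they have no row at all. Either way the route back is missing.

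**The case against.** The strongest objection concerns scope. The sentence under Table 5.3 reads "deemed related to trametinib (i.e. peripheral and periorbital edema) with the exception of the" eight events, so a literal reader could say that the general table covers only edema and there is no overlap. That does not stand: if only edema were covered, exempting rash, diarrhea and six other events would be pointless.

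A second objection is that a specific table ordinarily overrides a general one. That is a sensible habit of reading, but the protocol does not state it, and its exception list points the other way. Nor can Section 5.2.9 be presumed to control throughout. Its pneumonitis row discontinues for any treatment-related grade, where Table 5.10 continues at Grade 1. Its QTc row resumes at a lower level, where Table 5.9 restarts at the current one.

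Other objections do limit the point, because a reader might infer more than the documents support:

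- *That the tables are opposed at every grade.* They are not. Grade 3 bradycardia is a gap in Table 5.15, which Table 5.3 could fill, rather than a contradiction.
- *That Grade 1 bradycardia is continue against omit.* For an asymptomatic event the omit instruction cancels itself and the result is continuation, as in Table 5.3. It cannot be counted both as opposed and as self-cancelling. Whether such an event is clinically significant enough for Table 5.3 is also open.
- *That all Grade 3 fatigue differs by a full dose level.* Table 5.3 attaches the reduction to a restart, and interruption is optional. If dosing was not interrupted, maintaining it is a tenable reading of both tables; beyond 7 days both reduce.

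**Conclusion.** The concern holds as a drafting inconsistency with clinical consequences. There are two conflicts between tables (Grade 4 bradycardia with no contributing drug, and Grade 3 fatigue) and two unworkable or incomplete instructions within Table 5.15. This rests on reading the exception list as meaningful, and the conflicts arise only for events judged related and clinically significant.

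The number of patients affected cannot be stated. A reader might take the protocol's figure of at least 20% for fatigue and compute 27 × 0.20 = 5.4 patients. That is fatigue of any grade in a melanoma safety population, while the conflict exists only at Grade 3. The documents give no Grade 3 fatigue rate and no bradycardia rate, and bradycardia is not among the cardiac reactions listed in Section 4.1.1. What can be said is that, if all 27 patients are treated, each patient classified differently moves a reported proportion by 1/27 = 3.7 percentage points.

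The definition and test of ORR, the sample size, the power and the early stopping rule are untouched. The matter should be corrected, for patient safety and for the secondary interruption, reduction and discontinuation endpoints.

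**What to change.** In the text under Table 5.3, state which table governs fatigue, bradycardia and amylase/lipase, naming the three events. Do not exempt Section 5.2.9 as a whole: that would bring in its pneumonitis and QTc rows, which differ from Tables 5.10 and 5.9 and need their own reconciliation.

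Then reconcile Tables 5.3, 5.14 and 5.15 so that each event and grade has one workable action. In Table 5.15, reword the Grade 1 or 2 recovery condition so that it is not already met at onset, say what adjusting the trametinib dose means there, make clear which grades the concomitant-drug parenthesis covers, and state what follows Grade 3 bradycardia with no contributing drug. The clinical rule in each case is for the sponsor to choose.

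The cost is one added sentence and edits to a few table rows, made through the amendment process in Section 9.4 and sent to all sites. No new data are needed, and the sample size and statistical analysis do not change.

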### 5.3 Monitoring and Toxicity Management

Each patient receiving trametinib will be evaluable for safety. The safety parameters include all laboratory tests and hematological abnormalities, physical findings, and spontaneous reports of adverse events reported to the investigator by patients.

Each patient will be assessed periodically for the development of any toxicity as outlined in [Section 6 Study Procedures and Observations](#). Toxicity will be assessed according to the NCI [CTCAE v4.03](#). Dose adjustments will be made according to the system showing the greatest degree of toxicity.

We will monitor for potential adverse effects including but not limited to fatigue, dehydration, cytopenias, leukocytosis, nausea, vomiting, signs and symptoms of infection. In addition, we will monitor specifically for the following adverse events of special interest (please see corresponding subsections in Section 5.2 for acute toxicity management and dose modifications):

- Diarrhea (Section 5.2.2),
- Ejection fraction changes (Section 5.2.3),
- Hypertension (Section 5.2.4)
- Prolonged QTc (Section 5.2.5)
- Pneumonitis (Section 5.2.6),
- Visual changes (Section 5.2.7),
- Liver chemistry elevation (Section 5.2.8)

Acute toxicity will be managed by supportive care and/or delay of dose. Further management will depend upon the judgment of the treating clinician and may include dose reduction. Patients will also be monitored for visual changes and change in cardiac function and QTc as described below.

#### Ophthalmic Examination

Subjects are required to have a standard ophthalmic examination conducted by an ophthalmologist at baseline, week 4/Month 1 (prior to commencement of cycle 2), Month 6 and then annually thereafter unless clinically indicated sooner.

The exam will include visual acuity (best corrected), tonometry (intraocular pressure measurement), visual field examination, slit lamp biomicroscopy of the anterior segment (with special attention to inflammation) and the posterior segment, and indirect fundoscopic examination with special attention to possible retinal abnormalities. Optical coherence tomography is strongly recommended at scheduled visits, and if retinal abnormalities are suspected or noted. Other types of ancillary testing including color fundus photography and fluorescein angiography are also recommended if clinically indicated.

#### Cardiac monitoring

LVEF will be assessed by echocardiogram or multigated acquisition (MUGA) scan within 28 days prior to initiation of trametinib. The same cardiac monitoring procedure (either echocardiogram or MUGA scan) will be repeated at one month after initiation of trametinib, and then at every 3 month intervals while on treatment.

An electrocardiogram will be performed within 28 days prior to initiation of trametinib to assess QTc. An electrocardiogram will be repeated on Cycle 1 Day 1, at one month after initiation of trametinib, and then at every 3 month intervals while on treatment.

## 6 Study Procedures and Observations

### 6.1 Schedule of Procedures and Observations

The study-specific assessments are detailed in this section and outlined in [Section 6 Schedule of Study Procedures and Assessments](#). Screening assessments must be performed within 28 days prior to the first dose of investigational product. Any results falling outside of the reference ranges may be repeated at the discretion of the investigator. All on-study visit procedures are allowed a **window of  $\pm 3$  days** unless otherwise noted. Treatment or visit delays for public holidays or weather conditions do not constitute a protocol violation.

A written, signed, informed consent form (ICF) and a Health Insurance Portability and Accountability Act (HIPAA) authorization must be obtained before any study-specific assessments are initiated. A copy of the signed ICF will be given to the subject and a copy will be filed in the medical record. The original will be kept on file with the study records.

All patients who are consented will be registered in OnCore®, the UCSF Helen Diller Family Comprehensive Cancer Center Clinical Trial Management System (CTMS). The system is password protected and meets HIPAA requirements.

#### 6.1.1 Pretreatment Period

##### 6.1.1.1 Screening Assessments

Visit Windows: The Screening procedures and assessments must be completed within 28 days of the Day 1 Visit.

- Physical examination
- Vital signs
- Complete medical history including history of prior treatments and any residual toxicity relating to prior treatment
- Baseline conditions assessment
- Performance status
- Disease assessment including imaging (CT or MRI) of chest/abdomen/pelvis and brain for tumor/lesion assessment
- Baseline medications
- Research tumor biopsy for biomarker analysis (to be paid for by study), unless deemed medically unsafe
- Complete blood count (CBC) with differential and platelet count
- Blood chemistry assessments, including:
  - Alkaline phosphatase, aspartate aminotransferase/alanine aminotransferase (ALT/AST), total bilirubin, calcium, phosphorus, blood urea nitrogen (BUN), creatinine, albumin, fasting glucose, potassium, sodium, chloride, bicarbonate.

- Coagulation assessment, including prothrombin time, partial thromboplastin time, international normalized ratio (PT/PTT/INR)
- Urinalysis
- Serum or urine pregnancy test within 3 days prior to the start of study drug for patients of child-bearing potential.
- Electrocardiogram (ECG) in triplicate
- Cardiac assessment (MUGA or TTE)
- Ophthalmic exam
- Specimen collection for biomarkers and banking

## 6.1.2 Treatment Period

### 6.1.2.1 Study Procedures, Cycle 1, Day 1

Visit Windows: Screening laboratory tests completed within 3 days of Cycle 1 Day 1 do not need to be repeated

- Physical examination
- Vital signs
- Performance status
- Evaluation of adverse events
- Concomitant medications
- Complete blood count (CBC) with differential and platelet count
- Blood chemistry assessment, including:  
Alkaline phosphatase, ALT/AST, total bilirubin, BUN, creatinine, fasting glucose, potassium, sodium, chloride, bicarbonate
- Coagulation assessment, including PT/PTT/INR
- Urinalysis
- Serum or urine pregnancy test
- Electrocardiogram (ECG) in triplicate
- Administration of Trametinib in clinic
- Blood collection for ctDNA and cfDNA biomarkers

### 6.1.2.2 Study Procedures Cycle 1 Day 8

- Evaluation of adverse events
- Concomitant medications
- Administration of Trametinib in clinic
- Blood collection for ctDNA and cfDNA biomarkers

### 6.1.2.3 Study Procedures Cycle 1 Day 15

- Evaluation of adverse events
- Concomitant medications
- Administration of Trametinib in clinic
- Blood collection for ctDNA and cfDNA biomarkers
- Ophthalmic exam prior to cycle 2 day 1

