- **Clarification:** Subjects with atrial fibrillation controlled (defined as not requiring change in cardiac drug dosing, emergency room visit, or hospital admission) for >30 days prior to dosing are eligible.
- History of acute coronary syndromes (including myocardial infarction and unstable angina), coronary angioplasty, or stenting within 6 months prior to study enrollment.
- History or evidence of current  $\geq$  Class II congestive heart failure as defined by New York Heart Association (NYHA).
- Treatment refractory hypertension defined as a blood pressure of systolic > 140 mmHg and/or diastolic > 90 mm Hg which cannot be controlled by anti-hypertensive therapy;
- Patients with intra-cardiac defibrillators.

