**Vascular disorders**

Very common: Hypertension  
 Hemorrhage. The majority of bleeding events were mild. Major events, defined as symptomatic bleeding in a critical area or organ, and fatal intracranial hemorrhages have been reported.  
 Common: Lymphedema  
 Hypotension

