#### **Monitoring of Hypertension**

All blood pressure assessments should be performed under the following optimal conditions:

- the subject has been seated with back support, ensuring that legs are uncrossed and flat on the floor
- the subject is relaxed comfortably for at least 5 minutes
- restrictive clothing has been removed from the cuff area and the right cuff size has been selected
- the subjects arm is supported so that the middle of the cuff is at heart level
- the subject remains quiet during the measurement.

In subjects with an initial blood pressure reading within the hypertensive range, a second reading should be taken at least 1 minute later, with the 2 readings averaged to obtain a final blood pressure measurement. The averaged value should be recorded in the eCRF.

Persistent hypertension is defined as an increase of systolic blood pressure (SBP) > 140 mm Hg and/or diastolic blood pressure (DBP) > 90 mm Hg in three consecutive visits with blood pressure assessments from two readings collected as described above. Visits to monitor increased blood pressure can be scheduled independently from the per-protocol visits outlined in the Schedule of Study Procedures and Assessments (Table 6.1). Ideally, subsequent blood pressure assessments should be performed within one week.

Asymptomatic hypertension is defined as an increase of SBP >140 mm Hg and/or DBP >90 mm Hg in the absence of headache, light-headedness, vertigo, tinnitus, episodes of fainting or other symptoms indicative of hypertension.

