**Management of Hypertension**

For subjects experiencing an increase in systolic and/or diastolic blood pressure that is persistent and may be associated with the study treatment, recommendations for the clinical management of hypertension are described in Table 5.8:

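### Blood pressure has no required check between Cycle 1 Day 1 and Cycle 2 Day 1, although patients attend clinic on Days 8 and 15; adding it at those visits is a cheap improvement

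*Combined protocol and SAP*

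**What the plan says.** Section 6.1.2.1 lists vital signs on Cycle 1 Day 1. The next two lists, "6.1.2.2 Study Procedures Cycle 1 Day 8" and "6.1.2.3 Study Procedures Cycle 1 Day 15", include neither vital signs nor a physical examination. Both contain adverse event review, concomitant medications, a ctDNA/cfDNA blood draw and "Administration of Trametinib in clinic"; Day 15 adds the ophthalmic examination due before Cycle 2. Vital signs return in section 6.1.2.4, Cycle 2 and beyond. Table 6.1 agrees: its vital-signs row is marked at screening, Cycle 1 Day 1, Day 1 of later cycles, end of treatment and follow-up, and is blank for the rest of Cycle 1. Footnote d of that table describes the safety assessments at clinic visits as adverse event assessment and a medication check.

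The side-effect list in section 4.1.1 has "Very common: Hypertension", a category defined there as 10% or more. Section 5.3 names hypertension among the events of special interest to be monitored, and refers to Section 6 for when toxicity is assessed. Section 5.2.4 explains how to measure blood pressure and states: "Asymptomatic hypertension is defined as an increase of SBP >140 mm Hg and/or DBP >90 mm Hg in the absence of headache". It also says: "Visits to monitor increased blood pressure can be scheduled independently from the per-protocol visits". For persistent rises that may be related to treatment, "recommendations for the clinical management of hypertension are described in Table 5.8".

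The hypertension exclusion in section 3.3.2 covers only pressure "which cannot be controlled by anti-hypertensive therapy".

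**The concern.** Asymptomatic hypertension is defined by the reading, so asking about symptoms on Days 8 and 15 cannot detect it. The plan nevertheless has rules that act on such readings. In Table 5.8, Scenario A starts or adjusts antihypertensive drugs. Scenario B, for higher asymptomatic values, adds possible interruption of trametinib and a restart one dose level lower. None of this can begin until someone takes a first reading.

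The gap falls where drug exposure is rising. Section 1.2.3 gives a mean accumulation ratio of 5.97 at 2 mg daily, with steady state apparently reached by Day 15. The last required blood pressure before Day 29 is taken on the day of the first dose. Patients whose hypertension is controlled on treatment may enroll, and their control on trametinib has no scheduled check before Day 29 either.

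What is at stake is timely detection of a known and manageable toxicity. It bears on safety monitoring and not on the response-rate analysis.

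**Working it through.** The protocol states no figure for this interval, so there is none to reproduce. The check is calendar arithmetic.

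**Inputs**
- Cycle length: 28 days (Table 5.1).
- Visit window: ±3 days (section 6.1, Table 6.1).
- Clinic visits without vital signs: Day 8 (window 5–11) and Day 15 (window 12–18).
- Planned enrollment: 27 (section 3.2).
- Assumptions: vital signs, which the protocol does not define, include blood pressure; the first dose is on Day 1.

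**Current schedule**
- Cycle 2 Day 1 = 1 + 28 = Day 29, window 26–32.
- Gap without a required reading = 29 − 1 = 28 days nominally; 26 − 1 = 25 to 32 − 1 = 31 with the window.
- Required readings inside that gap: 0. Clinic visits inside it: 2.

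**With readings on Days 8 and 15**
- First required on-treatment reading: Day 8 instead of Day 29.
- Nominal intervals: 8 − 1 = 7, 15 − 8 = 7 and 29 − 15 = 14 days. The longest falls from 28 to 14.
- Worst case within windows: 32 − 12 = 20 days, against 31 now.

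**How much earlier a rise could first be detected**

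| Pressure raised | Nominal gain | Shortest, with windows | Longest, with windows |
|---|---|---|---|
| By the Day 8 visit | 29 − 8 = 21 days | 26 − 11 = 15 | 32 − 5 = 27 |
| After Day 8, by the Day 15 visit | 29 − 15 = 14 days | 26 − 18 = 8 | 32 − 12 = 20 |
| After the Day 15 visit | 0 | 0 | 0 |

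The 21 and 14 are two separate nominal values, one for each onset period, and not the ends of a continuous range.

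**Whether other text closes the gap**
- Section 5.3 sets no blood pressure timetable of its own; it points back to Section 6.
- The extra visits in section 5.2.4 are for pressure that is already increased, so they presuppose a raised reading.
- Section 5.2.4 and footnote a of Table 5.8 define persistence differently. Under either definition a first reading is needed. Scenario B does not require persistence for its asymptomatic thresholds of 160 mmHg systolic or 100 mmHg diastolic, but it too needs a reading.

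**Number of added readings**
- Initial readings: 2 visits × 27 patients = 54.
- Section 5.2.4 requires a second reading when the first is in the hypertensive range, so the ceiling is 2 × 2 × 27 = 108.

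**The case against.** The strongest reply is that this is a choice and not an error. Text and table agree, no stated standard is breached, and section 5.3 promises only periodic assessment, which a reading on Day 1 of each cycle provides. The same 28-day interval applies in later cycles. Days 8 and 15 look deliberately light, without physical examination or safety laboratory tests. Adverse events are reviewed on both days, the definition in section 7.3.1 includes signs, and a site may take a blood pressure whenever it sees reason to. For milder asymptomatic cases Table 5.8 continues trametinib at the same dose, and in Scenario B interruption is only if clinically indicated. Nothing in the documents shows that finding hypertension two or three weeks sooner changes an outcome.

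Much of this stands. The schedule is internally consistent, and a reader who inferred a contradiction between the lists and the table, or a breach of the protocol's own monitoring promise, would be wrong. It would also go too far to say that a 28-day interval is inadequate in itself. What remains is narrower. Later cycles follow at least one on-treatment reading, whereas Cycle 1 has none before Day 29 and is when exposure builds up. Leaving the measurement to site discretion may give different practice across centers. The patient is already in the clinic.

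**Conclusion.** This is an optional, low-cost improvement to safety monitoring. As written, asymptomatic hypertension has no required on-treatment detection point for 28 nominal days (25–31 with the window). Readings at the two existing visits would bring first possible detection forward by a nominal 21 days (15–27 with windows) for a rise present by Day 8, by 14 days (8–20) for one that appears after Day 8 and by Day 15, and not at all for a later rise.

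Three stronger readings are tempting, and the documents do not support them.
- *Hypertension would be missed.* Sustained hypertension would still be found at Cycle 2 Day 1; it is found late and not lost.
- *An average gain or a number of affected patients can be stated.* The documents give no onset timing. The frequency of at least 10% comes from a melanoma safety population and is not tied to any study day, so it cannot be turned into a count by Day 15.
- *The efficacy result is affected.* Nothing links this gap to the objective response rate, and no such effect is claimed.

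The conclusion assumes that vital signs include blood pressure. If they did not, no routine blood pressure would be scheduled anywhere and the gap would be larger. Confidence is high for the schedule facts and the arithmetic. The clinical importance of earlier detection cannot be sized from the documents.

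**What to change.** Add vital signs, stating that they include blood pressure, to the Day 8 list (6.1.2.2), the Day 15 list (6.1.2.3) and those two cells of the vital-signs row in Table 6.1. The measurement method in section 5.2.4 can apply unchanged.

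The cost is 54 initial cuff readings if all 27 patients attend both visits, and at most 108 if every first reading is raised and repeated. No new scheduled visit is needed. Raised readings may lead to unscheduled follow-up visits, because section 5.2.4 prefers a further assessment within one week and the procedure lists have no visit between Day 15 and Cycle 2 Day 1. Some patients would start or change antihypertensive treatment, or have trametinib interrupted or reduced under Table 5.8, earlier than now.
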